3.2 Randomization

Approximately 150 eligible subjects with moderate to severe plaque psoriasis will be randomized into this study. Subjects will be randomized in a 1:1:1 ratio (approximately 50 subjects per treatment group) to receive JTE-451 200 mg BID (400 mg/day), JTE-451 400 mg BID (800 mg/day) or placebo BID. Randomization will be stratified based on prior exposure to biologic therapy (i.e., biologic-naïve vs. biologic-experienced subjects) and body weight (i.e., <90 kg vs. ≥90 kg at Visit 2).

An Interactive Web Response System (IWRS) will be employed for the randomization activities. It will use a stratified randomization algorithm that takes into account the strata specified above.

The randomization code will be controlled by an unblinded member of the Sponsor or designee who will provide the randomization code to select laboratories (see [Protocol Section 3.7.8](#)).

4. SUBJECT POPULATIONS

4.1 Safety Population

The safety population consists of the randomized subjects who receive at least one dose of the study drug.

4.2 Intent-To-Treat (ITT) Population

The ITT population consists of all subjects who are randomized at Visit 2. Subjects will be analyzed according to the treatment to which they were assigned, even if subjects do not take the assigned treatment, do not receive the correct treatment, or otherwise do not follow the protocol.

4.3 Per Protocol (PP) Population

The PP population is a subset of the ITT population in which subjects do not have any major protocol deviations as listed below:

1. Dosing compliance not in 80%-120% (based on actual dosing period)
2. Subject's last dose not between Days 90-134
3. Subject did not take 360-536 tablets in total
4. >4 days between last dose and last non-follow-up efficacy assessment
5. Not meeting Inclusion Criterion #2, #3 or #4
6. Meeting Exclusion Criterion #1, #2, #3, #4, #5 (details shown below) or #10
7. Subject took “key” prohibited concomitant medications or had unstable background therapy that could potentially affect efficacy results/interpretation
 - Use of restricted medications listed in Table 2 of the protocol in the prohibited period
 - Use of prohibited medications listed in Table 4 and Table 5 of the protocol in the prohibited period. The exclusion decision will be made based on the review of the individual case and will be documented
8. Subject took incorrect study medication, e.g. due to incorrect drug dispense
9. Significant procedural deviations/non-compliance that could potentially affect efficacy results/interpretation

A pre-analysis meeting will take place after all data have been entered into the database and cleaned, but before the release of the randomization code, to identify the PP population. The decisions made to select the PP population will be documented.

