3.5.5 Study Restrictions

3.5.5.1 Previous and Concomitant Medication Restrictions

3.5.5.1.1 Prohibited Psoriasis Therapy and Immunomodulation Therapy

[figure not shown]
Use of the following therapies will NOT be allowed during the Prohibited Period as described in [Table 2](#).

Table 2. Psoriasis Therapy and Immunomodulation Therapy Restrictions

Prohibited Period	Medication(s)
24 weeks prior to Visit 2 till after the last study visit (Visit 8)	
• IL-12/IL-23p40 inhibitor (e.g., ustekinumab)• IL-23p19 inhibitor (e.g., guselkumab, mirikizumab, risankizumab, tildrakizumab)
12 weeks (or 5 times the PK half-life, whichever is longer) prior to Visit 2 till after the last study visit (Visit 8)	
• Biologic agents other than above (including marketed or investigational)• Investigational systemic therapies
28 days or 5 times the PK half-life (whichever is longer) prior to Visit 2 till after the last study visit (Visit 8)	
• Acitretin• Methotrexate• Cyclosporine• Apremilast• Oral/parental corticosteroids (including intramuscular or intraarticular administration)• Tofacitinib• Fumaric acid ester• Other immunomodulating systemic treatment• Psoralen plus ultraviolet A (PUVA) therapy• Ultraviolet A (UVA) therapy• Ultraviolet B (UVB) therapy• Investigational topical therapies
14 days prior to Visit 2 till after the last study visit (Visit 8)	
• Topical corticosteroids• Topical vitamin A or D analog preparations• Anthralin• Topical calcineurin inhibitors (e.g., cyclosporine)

Use of one (1) topical non-medical moisturizer (e.g., Cetaphil®) will be allowed during the study, however it will be prohibited within 12 hours prior to the study visit.

Note: If a subject develops significant clinical exacerbation of their psoriasis at any time during the entire duration of the study, study drug may be withdrawn and the subject will be treated clinically per existing standard of care.

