6.4 Efficacy Analysis

Analyses of primary and secondary efficacy parameters will be performed for both the ITT and PP populations, respectively.

For efficacy analyses, the JTE-451 treatment period is defined as the time period from the first dose of study drug to the last dose of study drug plus 4 days. The EOT value is defined as the last value taken during the JTE-451 treatment period. For PASI-50/75/90 and sPGA response analyses at EOT, if 10% or more subjects take any other psoriasis treatment that is listed in the protocol Section 3.5.5.1.1, a sensitivity analysis will be conducted using an alternative EOT value. The data used for the alternative EOT value determination will be up to and excluding the start of the other psoriasis treatment. The alternative EOT value will be the last value within 4 days after the last dose of JTE-451 in this data cutoff.

All analyses will be performed two-sided at the 5% significance level. No formal multiple comparison adjustment will be made for secondary efficacy parameters. The estimated treatment

effect (relative to placebo) from the model, along with a two-sided 95% confidence interval (CI) and p-value, will be tabulated where appropriate.

Graphical presentations of the treatment profile will be provided for the primary and secondary efficacy parameters. Sensitivity analysis and model fit assessment may be conducted, and data transformation may be employed if appropriate.

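### The PP rule, read literally, can drop a subject for psoriasis therapy started after the EOT PASI is measured; SAP 4.3 item 7 needs a cut-off at EOT

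*SAP*

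**What the plan says.** SAP 4.3 defines one PP population by a list of major deviations. Item 7 covers key prohibited medications, or a subject who "had unstable background therapy that could potentially affect efficacy results/interpretation". Two bullets follow. The first is "Use of restricted medications listed in Table 2 of the protocol in the prohibited period". The second covers Tables 4 and 5 of the protocol, and only there does the SAP add: "The exclusion decision will be made based on the review of the individual case and will be documented". PP membership is settled at a documented meeting held after data cleaning "but before the release of the randomization code, to identify the PP population".

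Protocol 3.5.5.1.1, Table 2, has four rows with different starting points but the same end. The row for IL-12/23 and IL-23 inhibitors reads "24 weeks prior to Visit 2 till after the last study visit (Visit 8", and the row for topicals reads "14 days prior to Visit 2 till after the last study visit (Visit 8". The note below the table foresees a significant exacerbation at any point in the study, in which case "study drug may be withdrawn and the subject will be treated clinically per existing standard of care".

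SAP 6.4 takes the EOT value as the last one between first dose and last dose plus four days. It adds: "Analyses of primary and secondary efficacy parameters will be performed for both the ITT and PP populations, respectively". SAP 6.4.2 leaves the follow-up visit out of the GEE and MMRM models. SAP 5.2.2 lists Week 20 among the time points for secondary parameters.

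**The concern.** An analysis set for an outcome fixed at EOT should not depend on what happens after EOT. Here it can. A subject may take all 16 weeks of drug, have a valid Visit 7 PASI, and begin a topical corticosteroid in Week 18. On the literal rule that subject is lost to the PP analysis of PASI-75 at EOT. The same subject is lost to the PP GEE and MMRM analyses, which contain no follow-up data that the exclusion could protect.

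Whether someone starts treatment after Visit 7 may well be related to how the skin responded by Visit 7. If so, the rule selects on the outcome. At stake is the usefulness of the PP results as a check on the ITT result, and the number of subjects left in them.

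The SAP is more careful elsewhere. Item 4 of the same list refers only to the last efficacy assessment outside follow-up. The alternative-EOT sensitivity analysis in SAP 6.4 cuts a subject's data at the start of other psoriasis treatment and keeps the subject. A Week 18 starter's value would be unchanged there.

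**Working it through.** **1. Timing (nominal days).** The last dose is taken the day before Visit 7 (Day 112), so on Day 111. The EOT window closes on Day 111 + 4 = Day 115. The Table 2 restriction runs past Visit 8 (Day 140). For at least 140 − 115 = 25 days, therapy can trigger item 7 but cannot affect the EOT value.

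**2. Inputs.**
- From SAP 6.1: 50 subjects per group and 15-20% discontinuation. At 20%, 50 × 0.80 = 40 completers per arm. The public text shows neither the response rates nor the power behind the 50, so that figure cannot be reproduced. Nothing below depends on it.
- From SAP 4.3 item 2: a last dose before Day 90 already excludes a subject, so the item 7 problem concerns mainly completers.
- Assumed, for illustration: EOT PASI-75 of 40% (active) and 10% (placebo) among completers, and the shares starting Table 2 therapy after EOT.

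**3. Formulas.** Let p be the EOT response rate. Let n and r be the shares of non-responders and responders who start Table 2 therapy after EOT and are removed.
- PP rate = p(1−r) / [p(1−r) + (1−p)(1−n)]
- PP odds = [p/(1−p)] × (1−r)/(1−n)
- PP odds ratio = full odds ratio × [(1−r)/(1−n)] in the active arm ÷ [(1−r)/(1−n)] in the placebo arm

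If n and r are the same in both arms, the last two factors cancel and the odds ratio does not move. The same holds within each stratum of the CMH analysis.

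**4. Results with 40 completers per arm (expected counts).**

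| Removed after EOT | Placebo PP rate | Active PP rate | Difference (points) | Odds ratio |
|---|---|---|---|---|
| Nobody | 4/40 = 10.0% | 16/40 = 40.0% | 30.0 | 6.0 |
| 20% of everyone, whatever the response | 3.2/32 = 10.0% | 12.8/32 = 40.0% | 30.0 | 6.0 |
| 10% of non-responders, both arms | 4/36.4 = 11.0% | 16/37.6 = 42.6% | 31.6 | 6.0 |
| 20% of non-responders, both arms | 4/32.8 = 12.2% | 16/35.2 = 45.5% | 33.3 | 6.0 |
| 30% of non-responders, both arms | 4/29.2 = 13.7% | 16/32.8 = 48.8% | 35.1 | 6.0 |
| Non-responders: 30% active, 10% placebo | 4/36.4 = 11.0% | 16/32.8 = 48.8% | 37.8 | 7.7 |
| Non-responders: 10% active, 30% placebo | 4/29.2 = 13.7% | 16/37.6 = 42.6% | 28.9 | 4.7 |
| 20% of non-responders in both arms, plus 20% of active responders | 4/32.8 = 12.2% | 12.8/32 = 40.0% | 27.8 | 4.8 |

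For example, 7.7 is (16/16.8) ÷ (4/32.4), and 4.7 is (16/21.6) ÷ (4/25.2).

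**5. Size of the PP set.** With 20% of non-responders removed in both arms, the pair of arms loses 7.2 + 4.8 = 12 of 80 completers, or 15%. Protocol 3.8.4 repeats the primary analysis on PP if PP drops 20% or more of ITT, which is 0.20 × 150 = 30 subjects. If 15% discontinue and all of them fall out of PP (an assumption), 22.5 are already gone and 7.5 more reach the trigger. Follow-up starters would count towards it. SAP 6.4 plans the PP analyses without that condition.

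**The case against.** The best case for the rule as it stands has four parts.

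First, the opening words of item 7 refer to an effect on efficacy results or interpretation, and a Week 18 topical has none on an EOT value. The blinded meeting could keep the subject on that ground. This is a possible reading, so it goes too far to infer that every follow-up starter is automatically removed. It does not settle the matter, though. There is one PP set, Week 20 efficacy is also analysed, and follow-up therapy can affect Week 20. The sentence on individual review belongs to the Table 4 and 5 bullet. Blinding prevents choices made by arm, but it does not stop a fixed rule from selecting on outcome.

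Second, the exclusion serves a purpose at Week 20. That stands, and it is why the remedy should keep the protection there.

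Third, the planned primary measure is the CMH adjusted odds ratio, which is unmoved when removal depends on response alone. That also stands.

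Fourth, starting therapy need not mean non-response. Protocol 1.3.2 says that the drug clears within about a day, so active-arm responders who relapse may start treatment too, and the last row of the table then lowers the odds ratio. A reader might infer that the rule inflates the drug's apparent effect. The documents do not support any fixed direction.

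**Conclusion.** The gap in the text is real and its consequence is limited. Item 7 has no cut-off at EOT, so PP membership for an EOT outcome can turn on a later event, and nothing in the SAP clearly exempts that case.

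Starts unrelated to response only shrink PP. Starts among non-responders raise both PP response rates and change the risk difference. The planned odds ratio moves only if starts also differ by arm for the same response status, and then in either direction: from 6.0 to 7.7 or 4.7 under the assumed 40% and 10% with 30% against 10% of non-responders starting. Those response rates and shares are illustrations, because the documents give no rate of follow-up starts.

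It would be wrong to conclude that the trial's main result is at risk. The ITT analysis keeps every randomised subject and is untouched. The effect is confined to the PP analyses and, under the protocol's wording, to the 20% trigger.

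**What to change.** Add to SAP 4.3, item 7, before the pre-analysis meeting: for EOT and on-treatment analyses, Table 2 use is a major deviation only if it falls within the prohibited period and no later than the subject's EOT assessment. Use that starts after the EOT assessment does not remove the subject from PP. That subject's Week 20 values alone are excluded or flagged in the PP Week 20 analyses.

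Item 6 needs no matching edit, since Exclusion Criterion 5 is an entry criterion.

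The cost is one sentence and one extra flag for the Week 20 PP analyses. Assessment dates and concomitant medication records are already collected. Which therapies are restricted, and for how long, does not change.

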4.4 Pharmacokinetic (PK) Population

The PK population consists of the randomized subjects who receive at least one dose of JTE-451 and have at least one usable JTE-451 plasma concentration measurement.

5. ANALYSIS PARAMETERS

5.1 Demographic and Baseline Characteristics

Demographic variables include age, gender, ethnic group, country, race, body weight, height and body mass index (BMI) at Screening Visit.

Baseline (last non-missing value prior to first dose) subject characteristics include but not limited to the following parameters: prior biologic therapy use (naïve or experienced), weight category (<90 kg or \geq 90 kg), age category (<65 years or \geq 65 years), prior exposure to oral systemic non-biologic therapies (yes or no), number of prior anti-psoriasis systemic treatment (biologic or non-biologic; 0, 1 or \geq 2), time from diagnosis, itch numeric rating scale (NRS, week average at one week prior to Day 1 dosing, i.e., Day -6 to Day 1), psoriasis body surface area (BSA), psoriasis area and severity index (PASI) score, static physician's global assessment (PGA) score, Skindex-16 questionnaire scale scores and overall score. [REDACTED]

Summary tables for demographic and baseline characteristics will be generated for the safety, ITT and PP populations, respectively.

5.2 Efficacy Parameters

5.2.1 Primary Efficacy Parameter

The primary efficacy parameter is the proportion of subjects achieving PASI-75 at end of treatment (EOT).

5.2.2 Secondary Efficacy Parameters

The secondary efficacy parameters (for which data will be evaluated at Weeks 2, 4, 8, 12, 16, 20 and EOT unless otherwise stated) are:

- Proportions of subjects achieving PASI-50/PASI-75/PASI-90;
- Percent change from baseline in PASI;
- Proportion of subjects achieving sPGA score of 0 or 1;
- Change from baseline in sPGA score;
- Percent change from baseline in BSA;
- Change from baseline in Skindex-16;
- Change from baseline in Itch NRS;
- Change from baseline in each domain score/questionnaire of Skindex-16.

5.2.4 Efficacy Parameters Calculation

5.2.4.1 Psoriasis Area and Severity Index (PASI)

The PASI is a quantitative rating score to assess the severity of psoriatic lesions based on the area coverage and plaque appearance. The PASI score will be derived as indicated in Table 2 below (refer to [protocol Section 3.5.6.2](#) for further details).

Table 2. The PASI Scoring

Body region	Erythema (E)	Thickening (plaque elevation, induration, I)	Scaling (desquamation, D)	Area score (based on true area %, A)*
Head (H) [†]	0=none 1=slight 2=moderate 3=severe 4=very severe	0=none 1=slight 2=moderate 3=severe 4=very severe	0=none 1=slight 2=moderate 3=severe 4=very severe	0 = 0% 1 = 1-9% 2 = 10-29% 3 = 30-49% 4 = 50-69% 5 = 70-89% 6 = 90-100%
Trunk (T) [‡]	0=none 1=slight 2=moderate 3=severe 4=very severe	0=none 1=slight 2=moderate 3=severe 4=very severe	0=none 1=slight 2=moderate 3=severe 4=very severe	0 = 0% 1 = 1-9% 2 = 10-29% 3 = 30-49% 4 = 50-69% 5 = 70-89% 6 = 90-100%
Upper limbs (U)	0=none 1=slight 2=moderate 3=severe 4=very severe	0=none 1=slight 2=moderate 3=severe 4=very severe	0=none 1=slight 2=moderate 3=severe 4=very severe	0 = 0% 1 = 1-9% 2 = 10-29% 3 = 30-49% 4 = 50-69% 5 = 70-89% 6 = 90-100%
Lower limbs (L) [§]	0=none 1=slight 2=moderate 3=severe 4=very severe	0=none 1=slight 2=moderate 3=severe 4=very severe	0=none 1=slight 2=moderate 3=severe 4=very severe	0 = 0% 1 = 1-9% 2 = 10-29% 3 = 30-49% 4 = 50-69% 5 = 70-89% 6 = 90-100%

Percentage (not score) of body region (not whole body) affected will be entered in the CRF

[†] Neck is assessed as part of the Head (H) body region.

[‡] Axillae and groin are assessed as part of the Trunk (T) body region.

[§] Buttocks are assessed as part of the Lower limbs (L) body region.

The PASI score is calculated using the following formula:

$$\text{PASI} = 0.1(\text{EH}+\text{IH}+\text{DH})\text{AH} + 0.2(\text{EU}+\text{IU}+\text{DU})\text{AU} + 0.3(\text{ET}+\text{IT}+\text{DT})\text{AT} + 0.4(\text{EL}+\text{IL}+\text{DL})\text{AL}$$

The PASI scores can range from 0, corresponding to no signs of psoriasis, up to a theoretic maximum of 72.0, corresponding to maximal signs of psoriasis. The calculated composite PASI score will be directly available in the corresponding database.

5.2.4.2 The PASI-50/PASI-75/PASI-90 Response Rate

The PASI-50/PASI-75/PASI-90 response rate will be calculated for Visits 3 through EOT respectively based on the PASI score collected by the Investigator.

The PASI-50/PASI-75/PASI-90 response is a dichotomous variable with a positive (= responder) or negative (= non-responder) outcome.

- PASI-50 is $\geq 50\%$ improvement from baseline
- PASI-75 is $\geq 75\%$ improvement from baseline
- PASI-90 is $\geq 90\%$ improvement from baseline

5.2.4.3 Static Physician's Global Assessment (sPGA)

The sPGA is used to determine the severity of subject's psoriatic lesion at a given time point. The psoriatic lesion will be graded for induration, erythema and scaling based on the scales below. The sPGA will be derived by the sponsor for all study visits.

The sum of the 3 scales will be divided by 3 to obtain the final sPGA score.

Induration (I)

0 = no evidence of plaque elevation
1 = barely palpable
2 = slight but definite elevation, indistinct edge
3 = elevated with distinct edges
4 = marked plaque elevation, hard/sharp borders

Erythema (E)

0 = no evidence of erythema (post inflammatory hyperpigmentation and/or hypopigmentation may be present)
1 = faint erythema
2 = light red coloration
3 = red coloration
4 = dusky to deep red coloration

Scaling (S)

0 = no evidence of scaling
1 = occasional fine scale
2 = fine scale predominates
3 = coarse scale predominates
4 = thick, coarse scale predominates

Add I+E+S = _____ /3 = _____ (Total Average)

Physician's Static Global Assessment based upon above Total Average

0 = Cleared, except for residual discoloration
1 = Minimal – majority of lesions have individual scores for I+E+S/3 that averages 1
2 = Mild – majority of lesions have individual scores for I+E+S/3 that averages 2
3 = Moderate – majority of lesions have individual scores for I+E+S/3 that averages 3
4 = Severe – majority of lesions have individual scores for I+E+S/3 that averages 4

Note: Scores should be rounded to the nearest whole number (e.g., if the total is <1.50 , the score should be 1; if the total is ≥ 1.50 , the score should be 2) except if the score is >0 and <1 , score should be treated as 1.

5.2.4.4 Psoriasis Body Surface Area (BSA)

The total BSA affected by plaque-type psoriasis will be estimated from the percentages of areas affected, including head, trunk, upper limbs and lower limbs. The psoriasis BSA will be derived by the Sponsor for all study visits.

The following calculations will be done: each reported percentage will be multiplied by its respective body region corresponding factor (head = 0.1, trunk = 0.3, upper limbs = 0.2, lower limbs = 0.4). The resulting 4 values will be added up to estimate the total BSA affected by plaque-type psoriasis.

5.2.4.5 Skindex-16

[figure not shown]
Skindex-16 is a 16-item, skin-related quality of life (QOL) questionnaire (refer to Appendix 2 of the protocol) and has three domain scores: symptoms, emotions, and functioning. Each 16-item QOL questionnaire will be reported on a scale of 0 to 6. Each raw score will be multiplied by 16.667, thus all responses will be transformed to a linear scale of 100 (i.e., from 0 [no effect] to 100 [effect experienced all the time]). A scale score is the average of non-missing items in a given scale as follows.

[figure not shown]
- Symptom scale score: average of items 1-4
- Emotions scale score: average of items 5-11
- Functioning scale score: average of items 12-16
- Overall score: average of 16 items

5.2.4.6 Itch Numeric Rating Scale (NRS)

The Itch NRS is a validated, self-reported instrument for measurement of itch intensity. It uses a 24-hour recall period and asks subjects to rate the worst itch intensity on an 11-point scale ranging from 0 (no itch) to 10 (worst itch imaginable).

The Itch NRS scores will be recorded by the subject using the e-diary once daily (before study drug administration once the subject is randomized) preferably at the same time of the day each day from Screening through the last visit.

5.3 Safety Parameters

5.3.1 Adverse Events (AEs)

An adverse event (AE) is any untoward medical occurrence in a patient or clinical investigation subject administered a pharmaceutical product and which does not necessarily have a causal relationship with this treatment.

Serious AE (SAE) is the AE that meets a criterion of the SAE definition per protocol. The severity of an AE is graded by Investigators referring to Common Terminology Criteria for Adverse Events (CTCAE) and translated into mild, moderate and severe and causality of AE is assessed in three categories “not related”, “possibly related” or “related”.

The Medical Dictionary for Regulatory Activities (MedDRA) Version 23.0 will be used to map verbatim AEs to preferred terms and their respective system organ classes. Adverse events will be characterized as either pre-treatment or treatment-emergent according to the criteria described in the following sections.

